9.10. Other Aspects

9.10.1. Confidentiality

The information in this and related documents is confidential and may not be disclosed, unless such disclosure is required by federal or other laws or regulations. In any event, persons to whom the information is disclosed must be informed that the information is confidential and may not be further disclosed by them.

Data generated as a result of this study are to be available for inspection on request of Blueprint Medicines' representative, ethics committees, or local regulatory agency, as required. Study data will be reported in aggregate and de-identified. Data will be stored in a secure database and shall be treated in compliance with all local applicable laws and regulations. Patients will not be contacted regarding assessments. If clarification or follow-up is needed regarding a potential ADR or medical information question reported during the study conduct, patients may be contacted, only by medical staff of the site involved in this PASS.

9.10.2. Protocol Amendment

Any amendment to the protocol will be created by Blueprint Medicines. Substantial amendments to the study protocol will be submitted to the Pharmacovigilance Risk Assessment Committee (PRAC) and independent ethics committees (IECs), in accordance with GVP Module VIII Addendum I.

10. PROTECTION OF HUMAN SUBJECTS

10.1. Participant Information and Consent

The Investigator at each study center will ensure that the patient or his/her legally authorised representative is given full and adequate oral and written information about the nature, purpose, possible risk, and benefit of the study. Patients must also be notified that their participation is voluntary and that they are free to discontinue from the study at any time. The patient must be given the opportunity to ask questions and allowed time to consider the information provided.

Patients or their legally authorised representative will be required to sign a statement of informed consent that meets the requirements of 21 CFR 50, local regulations, ICH guidelines, HIPAA requirements, where applicable, and the IRB/IEC or study center. Remote consent by phone or mail may be considered where a patient is unable to meet with the investigator in person due to logistical or other reasons. For those patients that have discontinued avapritinib treatment and/or were lost to follow-up and consent cannot be obtained, the Investigator will consult their IRB/IEC for guidance on accessing these patients' data retrospectively.

The patient's signed and dated informed consent must be obtained before conducting any studyrelated procedures. The Investigator must maintain the original, signed consent form which includes the signature of the authorised person obtaining the informed consent. A copy of the signed form must be given to the patient.

The method of obtaining and documenting the informed consent and the contents of the consent will comply with ICH-GCP and all applicable regulatory requirement(s). The medical record must include a statement that written informed consent was obtained before the patient was enrolled in the study and the date the written consent was obtained.

Patients must be re-consented to the most current version of the ICF(s) during their participation in the study.

10.2. Participant Withdrawal

Participation in this study is voluntary and patients may withdraw from the study at any time without prejudice. If the patient withdraws or is withdrawn, the reason will be collected in the eCRF. The ICF will explain that in case of withdrawal, all study data collected before withdrawal will be kept in the study database.

The Sponsor reserves the right, at any time, to discontinue enrolment of additional patients into the study, at any site; or to discontinue the study, for medical or administrative reasons.

10.3. Data Protection

Each patient will be assigned a unique identifier by the Sponsor. Any patient records or datasets that are transferred to the Sponsor will contain the identifier only; patient names or any information which would make the patient identifiable will not be transferred.

The patient must be informed that his/her personal study-related data will be used by the Sponsor in accordance with local data protection law. The level of disclosure must also be explained to the patient.

The patient must be informed that his/her medical records may be examined by Clinical Quality Assurance auditors or other authorised personnel appointed by the Sponsor, by appropriate IRB/IEC members, and by inspectors from regulatory authorities.

10.4. Independent Ethics Committee

It is the responsibility of Blueprint Medicines and the investigators to have prospective approval of the study protocol, protocol amendments, and other relevant documents (e.g., ICFs), if applicable, from the IEC.

10.5. Ethical conduct of the study

The study will be conducted in accordance with ethical principles founded in the Declaration of Helsinki (version 2008) and applicable legal and regulatory requirements and related guidances, especially Directive 2001/83/EC, Regulation (EC) No 726/2004 (REG) and Commission Implementing Regulation (EU) No 520/2012 (IR) as detailed in Good Pharmacovigilance Practices (GVP) Modules V, VI and VIII. For scientific purpose, value, and rigor the study will follow generally accepted research practices described in the EMA European Network of Centres for Pharmacoepidemiology and Pharmacovigilance (ENCePP) Guide on Methodological Standards in Pharmacoepidemiology, the ENCePP check-list for study protocol, Good Pharmacoepidemiology Practices (GPP) issued by the International Society for Pharmacoepidemiology (ISPE), and Good Epidemiological Practice (GEP) guidelines issued by the International Epidemiological Association.

This study has been registered in the EU-PAS Register (EUPAS41969).

The study will be submitted and supervised by the PRAC. The IRB/IEC will review all appropriate study documentation in order to safeguard the rights, safety, and well-being of the patients. The study will only be conducted at sites where IRB/IEC approval has been obtained.

10.6. Record Retention

The Investigator will maintain all study records according to ICH-GCP and applicable regulatory requirement(s). Records will be retained for at least 25 years or according to applicable regulatory requirement(s). If the Investigator wishes to withdraw from the responsibility of keeping the study records, Sponsor must be notified promptly in writing of such potential custodial change. The notification must include the name, contact information, new location of records, and any other pertinent information. Sponsor must approve such transfer in writing, which will not be unreasonably withheld, before Investigator is released of any obligations regarding such records. Custody must be transferred to a person willing to accept the responsibility.

11. MANAGEMENT AND REPORTING OF ADVERSE EVENTS/ADVERSE REACTIONS

11.1. Definitions

11.1.1. Adverse Event (AE)

An AE is defined as any untoward medical occurrence in a patient or clinical investigation subject administered a pharmaceutical product and which does not necessarily have a causal relationship with this treatment.

An AE can therefore be any unfavourable and unintended sign (e.g. an abnormal laboratory finding), symptom, or disease temporally associated with the use of a medicinal product, whether or not considered related to the medicinal product.

11.1.2. Serious Adverse Event (SAE)

An SAE is an adverse event which results in death, is life threatening, requires in-patient hospitalisation or prolongation of existing hospitalisation, results in persistent or significant disability or incapacity, or is a congenital anomaly/birth defect. Life-threatening in this context refers to a reaction in which the patient was at risk of death at the time of the reaction; it does not refer to a reaction that hypothetically might have caused death if more severe.

Medical and scientific judgement should be exercised in deciding whether other situations should be considered serious reactions, such as important medical events that might not be immediately life threatening or result in death or hospitalisation but might jeopardise the patient or might require intervention to prevent one of the other outcomes listed above. Examples of such events are intensive treatment in an emergency room or at home for allergic bronchospasm, blood dyscrasias or convulsions that do not result in hospitalisation or development of dependency or abuse. Any suspected transmission via a medicinal product of an infectious agent is also considered a serious adverse reaction.

All intracranial bleeding events should be considered serious regardless of severity.

11.1.3. Adverse Drug Reaction (ADR)

An ADR is defined as a response to a medicinal product which is noxious and unintended. Response in this context means that a causal relationship between a medicinal product and an adverse event is at least a reasonable possibility. Adverse reactions may arise from use of the product within or outside of the terms of the marketing authorisation or from occupational exposure. Conditions of use outside of the marketing authorisation include off label use, overdose, abuse and medication errors.

A serious adverse drug reaction meets both the definition of a SAE and an ADR.

11.1.4. Adverse Event of Special Interest (AESI)

An AESI is an adverse event of scientific and medical concern specific to the product or program, for which ongoing monitoring and rapid communication by the investigator to the sponsor can be appropriate. Such an event might warrant further investigation in order to characterise and understand it. AESIs selected for this study include cognitive effects and intracranial bleeding.

11.2. Adverse Event Severity

The investigator will use the following definitions to rate the severity of each recorded event. Severity and seriousness need to be independently assessed by the investigator for each event recorded on the CRF. Severity of events will be classified using NCI CTCAE Version 5.0 (see Table 2; of note a Semi-colon indicates 'or' within the description of the grade).

Grade 1	Mild; asymptomatic or mild symptoms; clinical or diagnostic observations only; intervention not indicated.
Grade 2	Moderate; minimal, local or noninvasive intervention indicated; limiting age appropriate instrumental activities of daily living (ADL).
Grade 3	Severe or medically significant but not immediately life-threatening; hospitalization or prolongation of hospitalization indicated; disabling; limiting self-care ADL.
Grade 4	Life-threatening consequences; urgent intervention indicated.
Grade 5	Death related to AE. ^a

Table 2:Severity rating adverse events

^a Death is not appropriate for some AEs and therefore not an option.

11.3. Relationship

The relationship of avapritinib to an AE will be determined by the investigator. Investigators should use their knowledge of the patient, the circumstances surrounding the event, the temporal sequence between the event and the use of avapritinib, and an evaluation of any potential alternative causes to determine whether an AE is considered to be related to avapritinib. The investigator will use the following definitions to assess the relationship of the AE to the use of the product:

Not Related: There is evidence against a reasonable causal relationship between the use of avapritinib and the occurrence of the event, either due to lack of temporal relationship, or lack of biological plausibility, or to the existence of more plausible alternative explanations for the occurrence of the event of concern such as underlying or concurrent illness.

Related: There is evidence in favour of a reasonable causal relationship between the use of avapritinib and the occurrence of the event due to plausible temporal relationship (the event occurred within a reasonable time after drug administration) and also biological plausibility, despite the potential existence of alternative explanations for the occurrence of the event of concern such as the event could not be reasonably explained by known characteristics including concomitant therapies and/or the AE abated after discontinuing the study drug.

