experienced by $\geq 1\%$ of patients were anaemia (4.3%), pleural effusion (1.7%), and acute kidney injury (1.3%). A total of 19.7% of patients with GIST discontinued avapritinib due to an AE, which appeared to be predominantly related to the patients' underlying disease. The most commonly ($\geq 1\%$) reported AEs leading to study drug discontinuation were disease progression (3.0%), general physical health deterioration (1.7%), and abdominal pain, acute kidney injury, anaemia, fatigue, and sepsis (1.3%). For these patients, 9.0% discontinued study drug due to an AE that was considered treatment-related. The following treatment-related AEs led to study drug discontinuation in >1 patient: fatigue (1.7%) and confusional state, encephalopathy, nausea, and vomiting (<1% each).

During clinical development, two AESIs were identified: intracranial bleeding and cognitive effects. Although the mechanism for these events is unclear, intracranial bleeding and cognitive effects have been reported with imatinib and other TKIs. (Feki et al. 2015; Shaw et al. 2017; Song et al. 2004)

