Intracranial bleeding (e.g., subdural haematoma, intracranial haemorrhage) occurred in 9 (1.6%) of the 550 patients with GIST who received avapritinib at starting doses of either 300 or 400 mg once daily. Intracranial bleeding was reported by 3% (7/250) of all patients in BLU-285-1101: 3 patients had a subdural haematoma (Grade 1, Grade 2 or Grade 3), 2 patients had an intracranial haemorrhage (Grade 1 or Grade 3) and 2 patients had a cerebral haemorrhage (Grade 3 or Grade 4). Consistent with the overall trend of a slightly less severe safety profile observed in the Phase III trial, intracranial bleeding was reported in 1% of all patients who received any dose of avapritinib in BLU-285-1303: 2 patients with Grade 4 intracranial haemorrhage and 1 patient with both a Grade 4 subdural haematoma and a Grade 4 intracranial haemorrhage. No fatal intracranial bleeding events were reported in either study. The mechanism by which avapritinib may cause events of intracranial bleeding are uncertain. Risk factors for intracranial bleeding include severe thrombocytopenia (platelet count <50,000/µl), vascular aneurysm, a history of intracranial haemorrhage within the prior year, and a history of a cerebrovascular accident or transient ischaemic attack. Appropriate risk minimisation measures including lower starting dose and restrictions for dose escalation might reduce the risk. It is recommended that avapritinib be permanently discontinued in patients with an observed intracranial bleeding event of any severity grade during treatment.

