Cognitive effects occurred in 182 (33%) of the 550 patients with GIST who received avapritinib at starting doses of either 300 or 400 mg once daily. Most cognitive effects were Grade 1 (89%), with Grade \geq 2 occurring in 11% of 550 patients. Memory impairment occurred in 20% of patients, <1% of these events were Grade 3. Cognitive disorder occurred in 12% of patients; <1% of these events were Grade 3. Confusional state occurred in 5% of patients; <1% of these events were Grade 3. Confusional state occurred in 5% of patients; <1% of these events were Grade 3. Encephalopathy occurred in <1% of patients; <1% of these events were Grade 3. SAEs of cognitive effects were reported for 7 of the 550 (1.3%) patients. Overall, 1.3% of patients required permanent discontinuation of avapritinib for a cognitive effect. Cognitive effects were reported by 46% of the patients in BLU-285-1101, most cases were mild-moderate AEs (90% Grade 1-2 AEs, 10% Grade 3 AEs). Consistent with the overall trend of a slightly less severe safety profile observed in the Phase III trial, cognitive effects were reported by 26% of the patients in BLU-285-1303, 95% Grade 1-2 AEs and 5% Grade 3 AEs. The early recognition and management of cognitive effects might explain the lower incidence in the Phase III trial as

AESIs of cognitive effects were higher in the 400 mg starting dose group compared to the 300 mg group in BLU-285-1101 (48% vs 39%). However, the median treatment duration for patients receiving avapritinib (any dose) in the Phase III trial was also considerably shorter (8.9 months) than in the Phase I trial (23.2 months). No fatal cognitive events were reported in either study. In the clinical development program, the probability of experiencing a cognitive effect increased over the first 7 to 8 months of treatment and then reached a plateau. Non-clinical mechanistic studies could not clearly identify the underlying mechanism for cognitive effects (i.e., memory impairment). Clinical factors associated with an increased likelihood of experiencing Grade \geq 2 cognitive effects include a medical history of cognitive effects, prior regorafenib use and age \geq 65 years. Brain imaging studies of patients experiencing cognitive effects effect symptoms during the clinical studies did not reveal any associated anatomical changes.

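### Section 11.3 sets a stricter test for a related event than the adverse drug reaction definition in 11.1.3, so one event can be a reaction under one section and Not Related under the other

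*Protocol*

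**What the plan says.** Section 11.3 tells the investigator to classify each event as Related or Not Related, using the definitions given there.

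- **Related** calls for evidence in favour of a reasonable causal relationship, based on "plausible temporal relationship (the event occurred within a reasonable time after drug administration) and also biological plausibility". The two elements are joined, so both are needed.
- **Not Related** calls for evidence against such a relationship, "either due to lack of temporal relationship, or lack of biological plausibility, or to the existence of more plausible alternative explanations". The three grounds are alternatives, so one is enough.

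Section 11.1.3 defines an ADR as a noxious and unintended response where "a causal relationship between a medicinal product and an adverse event is at least a reasonable possibility". It sets no condition on biological plausibility.

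The relatedness call is used in two places. Section 9.7.2 tabulates AEs by relationship to avapritinib as part of the primary endpoint. Section 11.4 asks sites to report non-serious ADRs to the sponsor within 30 calendar days.

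**The concern.** A post-authorisation safety study should be able to pick up toxicities that nobody expected. Such events often have no recognised biological explanation when they first appear. If the causality scale makes plausibility compulsory for Related, and lets its absence settle Not Related, these are the events it moves to the unrelated column. Section 11.1.3 would leave them open as reactions.

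At stake are the relationship breakdown of the AE tables and the route by which a non-serious reaction outside the AESI list reaches the sponsor. A statistical analysis plan cannot repair this later, because site investigators make the call from the protocol text.

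**Working it through.** No arithmetic applies. The check is to put one event through both sections and then trace what depends on the answer.

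**The test event.** It starts at a plausible time after dosing, has no stronger alternative explanation, is non-serious, is neither a cognitive effect nor an intracranial bleed, and has no recognised biological basis.

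| Question | 11.3 | 11.1.3 |
|---|---|---|
| Is plausible timing enough without biological plausibility? | No, both are required for Related | Not excluded; no plausibility condition is set |
| Can lack of plausibility alone decide against causation? | Yes, it is one of three alternative grounds for Not Related | No such ground is listed |
| Threshold | Evidence in favour of a reasonable causal relationship | At least a reasonable possibility |
| Result for the test event | Fails Related; meets a listed ground for Not Related | Can be an ADR |

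**Inside 11.3.** The opening paragraph asks investigators to weigh their knowledge of the patient, the circumstances, the temporal sequence and alternative causes. Biological plausibility is not named there. It first appears in the definitions, where it becomes decisive in both directions.

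**What depends on the call.**

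1. *AE tables by relationship (9.7.2).* The test event is counted as unrelated, so the related-event count is too low by that event.
2. *Thirty-day reporting (11.4).* The duty covers non-serious ADRs. By 11.1.3 the event is reportable. A site that has just marked it Not Related may not report it.
3. *Sponsor causality review (11.4).* The sponsor or its designee takes responsibility for causality assessment of serious events, AESIs and ADRs. A non-serious, non-AESI event marked Not Related need not enter that stream.

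**What does not depend on it.**

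1. *Collection.* Section 9.3 collects every AE regardless of causality, so the test event is still in the database.
2. *Overall rates.* The incidence rates in 9.7.2, overall and by system organ class and preferred term, count patients with an event whatever its attribution.
3. *Expedited reporting.* Section 11.4 requires serious events and AESIs to be reported within 1 business day, or no later than 3 calendar days, without reference to relatedness.

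**The case against.** The best defence is that 11.3 should be read as a whole. Not Related opens by asking for evidence against causation, and an unexplained mechanism is absence of evidence, not evidence against. Related may be chosen despite possible alternative explanations, and 11.3 mentions improvement after stopping the drug. Both definitions speak of a reasonable causal relationship, which is close to the language of 11.1.3. Section 11.3 is also the stated rule for the relationship call, while 11.1.3 only defines a term.

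This softens the point but does not remove it. The text itself names lack of plausibility as a form of evidence against causation. Even if a site sets that ground aside, the test event still fails the joint requirement for Related, and no third category exists. Nor is 11.1.3 idle, because 11.4 attaches a reporting duty to the term it defines.

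A reader might go further and infer that both AESIs would be classed Not Related. Section 7.1 does say that "The mechanism by which avapritinib may cause events of intracranial bleeding are uncertain" and that "Non-clinical mechanistic studies could not clearly identify the underlying mechanism for cognitive effects". The documents do not support that inference:

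- Section 11.3 asks for plausibility, not a known mechanism.
- Section 7.1 supplies class precedent: "Although the mechanism for these events is unclear, intracranial bleeding and cognitive effects have been reported with imatinib and other TKIs".
- Section 7.1 reports more cognitive effects at the 400 mg than at the 300 mg starting dose in BLU-285-1101 (48% vs 39%).
- Section 7.1 lists memory impairment (20%) among treatment-related events in the pooled trials. Whether those trials used the same causality wording is not stated.
- AESI reporting does not depend on relatedness, and 11.1.2 treats every intracranial bleed as serious.

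A reader might also try to size the effect from the 33% (182/550) with cognitive effects in 7.1. That is a rate of occurrence, not of related events, and nothing in the documents suggests that such events would be called unrelated.

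**Conclusion.** Wrong as written: sections 11.3 and 11.1.3 contradict each other on the causality threshold. Where they differ, 11.3 moves the event towards Not Related, the less cautious direction for a study whose primary objective is safety.

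The reach is narrow. It covers well-timed, non-serious, non-AESI events with no better explanation and no recognised biological basis. For these, the related-event tables would be understated, and the 30-day report and the sponsor's causality review could be missed. Total AE rates and the handling of serious events and AESIs stand.

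No numerical size can be given. The documents do not say how many such events to expect or how sites would classify them. The conclusion rests on taking the definitions in 11.3 at their word, and severity is minor.

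**What to change.** Align 11.3 with 11.1.3 by changing its two definitions:

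- **Related:** use the 11.1.3 threshold, that causation is at least a reasonable possibility. Judge it on time course, response to stopping the drug, alternative causes and, where known, biological plausibility. Plausibility then supports a judgement of Related but is not required for it.
- **Not Related:** delete lack of biological plausibility as a stand-alone ground. Keep the grounds of incompatible timing and a more plausible alternative cause.

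The cost is two sentences in 11.3 and a matching edit to any eCRF completion guidance. The downside is that somewhat more events will be classed as related and reported as ADRs. The change is best made before many events have been classified, because inconsistent site judgements are hard to repair afterwards.
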